1.3.5.2 Rationale for 4 cycles of combination therapy followed by durvalumab monotherapy

Long-term follow up on melanoma patients treated with ipilimumab, an anti-CTLA-4 targeting antibody (dosed every 3 weeks [q3w] for 4 doses and then discontinued), shows that patients responding to ipilimumab derive long-term benefit, with a 3-year OS rate of approximately 22%. Furthermore, the survival curve in this population reached a plateau at 3 years and was maintained through 10 years of follow up (Sangro et al., 2013; Schadendorf et al., 2015).

Similar data have been presented for other anti-PD-1/PD-L1 targeting antibodies:

Nivolumab (anti-PD-1) was dosed q2w for up to 96 weeks in a large Phase I dose-escalation and expansion study, and showed responses were maintained for a median of 22.94 months for

melanoma (doses 0.1 mg/kg to 10 mg/kg), 17 months for NSCLC (doses 1, 3, and 10 mg/kg), and 12.9 months for renal cell carcinoma patients (doses 1 and 10 mg/kg) at the time of data analysis (Gettinger et al., 2015). Furthermore, responses were maintained beyond treatment discontinuation in the majority of patients who stopped nivolumab treatment (either due to protocol specified end of treatment, complete response [CR], or toxicity) for up to 56 weeks at the time of data analysis (Topalian et al., 2014) MPDL3280a (anti-PD-L1) and the combination of nivolumab with ipilimumab, in which patients were dosed for a finite time period and responses maintained beyond treatment discontinuation have been reported (Wolchok et al., 2013).

Similar long term results may be expected with use of other immune-mediated cancer therapeutics including anti-CTLA-4 antibodies such as tremelimumab, anti-PD-L1 antibodies such as durvalumab, or the combination of the two.

The durvalumab + tremelimumab combination regimen will be administered for 4 doses Q4W followed by durvalumab monotherapy Q4W until disease progression, for up to a maximum further 8 doses unless other specific discontinuation criteria are met.

1.3.5.3 Rationale for fixed dosing

A population PK model was developed for durvalumab using monotherapy data from a Phase I study (study 1108; N=292; doses=0.1 to 10 mg/kg Q2W or 15 mg/kg Q3W; solid tumors). Population PK analysis indicated only minor impact of body weight (WT) on the PK of durvalumab (coefficient of ≤ 0.5). The impact of body WT-based (10 mg/kg Q2W) and fixed dosing (750 mg Q2W) of durvalumab was evaluated by comparing predicted steady state PK concentrations (5th, median and 95th percentiles) using the population PK model. A fixed dose of 750 mg was selected to approximate 10 mg/kg (based on median body WT of ~ 75 kg). A total of 1000 patients were simulated using body WT distribution of 40–120 kg. Simulation results demonstrate that body WT-based and fixed dosing regimens yield similar median steady state PK concentrations with slightly less overall between-patient variability with fixed dosing regimen.

Similarly, a population PK model was developed for tremelimumab using data from Phase 1 through Phase 3 (N=654; doses=0.01 to 15 mg/kg Q4W or Q90D; metastatic melanoma) (E. Wang et al., 2014). Population PK model indicated minor impact of body WT on PK of tremelimumab (coefficient of ≤ 0.5). The WT-based (1 mg/kg Q4W) and fixed dosing (75 mg/kg Q4W; based on median body WT of ~ 75 kg) regimens were compared using predicted PK concentrations (5th, median and 95th percentiles) using population PK model in a simulated population of 1000 patients with body weight distribution of 40 kg to 120 kg. Similar to durvalumab, simulations indicated that both body WT-based and fixed dosing regimens of tremelimumab yield similar median steady state PK concentrations with slightly less between-patient variability with fixed dosing regimen.

Similar findings have been reported by others (Narwal, Roskos, & Robbie, 2013; Ng, Lum, Gimenez, Kelsey, & Allison, 2006; D. D. Wang, Zhang, Zhao, Men, & Parivar, 2009; S. Zhang, Shi, Li, Parivar, & Wang, 2012). Wang and colleagues investigated 12 monoclonal antibodies and found that fixed and body size-based dosing perform similarly, with fixed dosing being better for 7 of 12 antibodies(D. D. Wang et al., 2009). In addition, they

investigated 18 therapeutic proteins and peptides and showed that fixed dosing performed better for 12 of 18 in terms of reducing the between-patient variability in pharmacokinetic/pharmacodynamics parameters (S. Zhang et al., 2012).

A fixed dosing approach is preferred by the prescribing community due to ease of use and reduced dosing errors. Given expectation of similar pharmacokinetic exposure and variability, we considered it feasible to switch to fixed dosing regimens. Based on average body WT of 75 kg and the pharmacodynamic data as summarized above, a fixed dose of 1500 mg Q4W durvalumab (equivalent to 20 mg/kg Q4W) and a fixed dose of 300mg tremelimumab once and a fixed dose of 1500 mg Q4W durvalumab and 75 mg tremelimumab Q4W(equivalent to 1mg/kg Q4W) is included in the current study.

1.4 Benefit-risk and ethical assessment

1.4.1 Potential benefits

1.4.1.1 Durvalumab + tremelimumab

It is hypothesized that durvalumab and tremelimumab may have a synergistic anti-tumor effect above what would be anticipated from their individual anti-tumor activity. We have seen in preclinical studies which show that combination therapy (dual targeting of PD-L1 and CTLA-4) has been shown in preclinical studies with a mouse model to cause tumor regression of

Other combinatorial trials using nivolumab (PD1 inhibitor) plus ipilimumab (CTLA-4) for stage III or IV measurable, unresectable melanoma have recently been reported with promising results. At the maximum tolerated combination dose—1mg/kg anti-PD1 plus 3 mg/kg ipilimumab every three weeks administered concurrently, 53% of patients had an objective response, all with tumor reduction of 80% or more. Adverse effects occurred in 53% of patients and were similar in quality and intensity to those observed with ipilimumab monotherapy. Sequential administration resulted in a lower response rate and lower toxicity rate.

1.4.1.2 DEB-TACE and Immunotherapy

Accumulating evidence also suggest that eliciting tumor-specific T-cell immune responses can potentiate current checkpoint inhibitor therapy. This was suggested in mice models with liver metastasis from colorectal cancer, where combined radiofrequency ablation and anti-PD1 treatment provided longer duration of tumor regression and survival than single treatment group (Shi L et al 2016). Additionally, CTLA-4 has an inhibitory effect of T cell activation, and blockade of its target ligand (B7) shows been shown to markedly enhance T cell activation and antitumor activity in animal models. Clinically, we know that liver-directed treatments such as DEB-TACE induce inflammatory response in patients, shown with rising cytokines levels and other inflammatory markers including neutrophils and lymphocytes obtained from peripheral blood samples (Xue et al. 2015)

1.4.2 Overall risks

Monoclonal antibodies directed against immune checkpoint proteins, such as programmed cell death ligand 1 (PD-L1) as well as those directed against programmed cell death-1 (PD-1) or cytotoxic T-lymphocyte antigen-4 (CTLA-4), aim to boost endogenous immune responses directed against tumor cells. By stimulating the immune system however, there is the potential for adverse effects on other tissues.

Most adverse drug reactions seen with the immune checkpoint inhibitor class of agents are thought to be due to the effects of inflammatory cells on specific tissues. These risks are generally events with a potential inflammatory or immune mediated mechanism and which may require more frequent monitoring and/or unique interventions such as immunosuppressants and/or endocrine therapy. These risks can include gastrointestinal AEs such as colitis and diarrhoea, pancreatitis, pneumonitis/interstitial lung disease (ILD), renal AEs such as nephritis and increases in creatinine, hepatic AEs such as hepatitis and liver enzyme elevations, skin events such as rash and dermatitis, endocrinopathies such as hypo- and hyper-thyroidism, hypophysitis, adrenal insufficiency, diabetes mellitus type I and diabetes insipidus, and neurotoxicities such as myasthenia gravis and Guillain-Barre syndrome.

1.4.2.1 Durvalumab

Risks with durvalumab include diarrhea, colitis, pneumonitis /ILD, encephalitis, endocrinopathies (hypo- and hyper-thyroidism, type I diabetes mellitus (which may present as diabetic ketoacidosis), diabetes insipidus, hypophysitis and adrenal insufficiency), hepatitis/hepatotoxicity/increases in transaminases, immune thrombocytopenia, neurotoxicities, nephritis/increases in creatinine, pancreatitis, rash/pruritus/dermatitis, myocarditis, infusion-related reactions, anaphylaxis, hypersensitivity or allergic reactions, pemphigoid, subcutaneous injection site reaction, and immune complex disease.

Further information on these risks can be found in the current version of the durvalumab IB.

In monotherapy clinical studies AEs (all grades) reported very commonly ($\geq 10\%$ of patients) are fatigue, nausea, decreased appetite, dyspnea, cough, constipation, diarrhea, vomiting, back pain, pyrexia, abdominal pain, anemia, arthralgia, peripheral edema, headache, rash, and pruritus. Approximately 8% of patients experienced an AE that resulted in permanent discontinuation of durvalumab and approximately 5% of patients experienced an SAE that was considered to be related to durvalumab by the study investigator.

The majority of treatment-related AEs were manageable with dose delays, symptomatic treatment, and in the case of events suspected to have an immune basis, the use of established treatment guidelines for immune-mediated toxicity (see the Dosing Modification and Toxicity Management Guidelines in Appendix 1).

A detailed summary of durvalumab monotherapy AE data can be found in the current version of the durvalumab IB.

1.4.2.2 Tremelimumab

Risks with tremelimumab monotherapy are GI effects (colitis, diarrhoea, enterocolitis and intestinal perforation), endocrine disorders (hypo and hyperthyroidism, hypophysitis and adrenal insufficiency), skin effects (rash, and pruritus), elevations in lipase and amylase, other gastrointestinal events e.g. ulcerative colitis, dehydration, nausea and vomiting; hepatic events including hepatitis, and liver enzyme elevations; pneumonitis and ILD; clinical manifestations of pancreatitis; nervous system events including encephalitis, peripheral motor and sensory neuropathies, Guillain-Barre and proximal muscle weakness; cytopenias including thrombocytopenia, anemia and neutropenia; infusion-related reactions, anaphylaxis, and allergic reactions; renal events including renal failure, acute kidney injury, nephritis, nephrotic syndrome, autoimmune nephritis and electrolyte abnormalities such as hypokalemia; autoimmune diseases including autoimmune arthritis, Sjögren's syndrome and giant cell temporal arteritis; hyperglycemia and diabetes mellitus; and pyrexia. Further information on these risks can be found in the current version of the tremelimumab IB.

Using pooled data from monotherapy clinical studies AEs (all grades) reported very commonly ($\geq 10\%$ of patients) were diarrhea, nausea, fatigue, pruritus, decreased appetite, rash, vomiting, dyspnea, constipation, cough, pyrexia, abdominal pain, decreased weight, headache, asthenia, and anaemia. Approximately 16% of patients experienced an AE that resulted in permanent discontinuation of tremelimumab and approximately 45% of patients experienced an SAE. A detailed summary of tremelimumab monotherapy AE data can be found in the current version of the tremelimumab IB.

1.4.2.3 Durvalumab + tremelimumab

The safety of durvalumab + tremelimumab combination therapy is being evaluated in the ongoing dose escalation and dose expansion Study 006, in patients with NSCLC, and has so far shown a manageable safety and tolerability profile.

The potential risks with the combination of durvalumab + tremelimumab are similar to those for durvalumab and tremelimumab monotherapy. Emerging data from study 006 and from combinations of other agents in the same class indicate an increased frequency and/or severity of some of these potential immune-mediated toxicities.

In durvalumab+tremelimumab combination studies at the dose of durvalumab 20mg/kg and tremelimumab 1mg/kg AEs (all grades) reported very commonly ($\geq 10\%$ of patients) are fatigue, diarrhoea, nausea, dyspnea, decreased appetite, pruritus, vomiting, anaemia, constipation, cough, abdominal pain, pyrexia, back pain, hyponatremia and rash.

Approximately 13% of patients experienced an AE that resulted in permanent discontinuation of study drug and approximately 13% of patients experienced an SAE that was considered to be related to durvalumab and tremelimumab by the study investigator.

A detailed summary of durvalumab + tremelimumab combination AE data can be found in the current version of the durvalumab IB.

1.4.2.4 Overall benefit-risk of DEB-TACE with Durvalumab + tremelimumab

Currently we do not have effective systemic treatment recommendation for patients with intermediate HCC, who are often outside the criteria for surgical resection but also not indicated for the FDA approved sorafenib. 2 year overall survival ranges from 30-40% at best with median survival ranging from 11-20months. This is a large subset of patients with HCC who can benefit from targeted immunotherapy while receiving locoregional treatment with DEB-TACE as standard of care. If our hypothesis proves to be true with clear benefit of combinatorial treatment, this will also increase the possibilities for patients with intermediate stage HCC to have enough tumor burden reduction to undergo curative treatments, such as resection or liver transplantation.

For this proposal, we will select those with compensated liver disease, with Child-Pugh score less than 7 (early B). The risk of side effects has been reviewed, and to prevent serious complications, we have designed this study to assess early for any adverse effects.

2. STUDY OBJECTIVE

2.1 Primary Objective

- To evaluate the objective response rate (ORR) of patients with intermediate stage HCC treated with anti-CTLA-4 (Tremelimumab) and anti-PD-L1 (Durvalumab) with transarterial chemoembolization (DEB-TACE), according to modified response evaluation criteria in solid tumors (mRECIST).

2.2 Secondary Objectives

- To assess the safety of combining DEB-TACE with durvalumab and tremelimumab in patients with intermediate stage HCC.

2.3 Exploratory Objectives

- To evaluate progression-free survival (PFS) and 6-month PFS of patients treated with the combination of durvalumab and tremelimumab with DEB-TACE.
- To evaluate the tumor response of non-targeted lesion evaluated by objective response (mRECIST).
- To evaluate a 2 year overall survival (OS) of patients treated with the combination of durvalumab and tremelimumab with DEB-TACE
- To determine the effect of combined immune checkpoint and DEB-TACE versus DEB-TACE only on tumor microenvironment by comparing pre- and post-treatment tissue samples and peripheral blood tumor biomarkers including T cell receptor repertoire and circulating tumor cells/ circulating tumor DNA.
- To explore potential molecular determinants of response, progression, and disease stability using next generation sequencing, other sequencing techniques, and other biomarkers.

3. STUDY DESIGN

This is an open-label, single institution, single arm study of combination treatment of durvalumab and tremelimumab in patients with intermediate stage HCC (BCLC B) undergoing trans-arterial chemoembolization.

Patients will be recruited from the Johns Hopkins Multidisciplinary Liver Cancer Clinic, general liver clinic, inpatient admissions with newly diagnosed HCC, and direct referrals to Interventional Radiology for DEB-TACE treatment. Once their diagnosis and staging is confirmed in Liver radiology tumor board as intermediate stage, patients will be screened for enrollment.

Enrolled patients will proceed with DEB-TACE procedure along with pre-treatment biopsy of tumor and surrounding non-tumor tissue. Following their DEB-TACE procedure, patients will be followed in 7-10 days in hepatology clinic with labs for any new decompensating signs or symptoms. If the patient does not have any ongoing new decompensation, they will proceed with a 2nd biopsy, followed by 1st infusion of durvalumab 1500mg and tremelimumab 300mg 2 weeks after DEB-TACE. This will be followed by durvalumab 1500mg q4weeks until progression of disease, the end of study, or maximum 13 cycles.

All patients will receive repeat DEB-TACE every 8 weeks if there is residual tumor that can be targeted. A third biopsy will be done after 2 doses of durvalumab infusion during their second DEB-TACE procedure at week 8, unless the patient has CR.

Patients will have an MRI (or CT if contraindicated) at Week 6 and Week 14, then every 3 months unless additional DEB-TACE is needed. Patients who are clinically stable at initial disease progression may continue to receive study treatment until PD is confirmed on a follow-up scan (confirmed PD) if they do not show any significant toxicities. Patients will get a confirmatory scan, following the assessment of PD, at the next scheduled visit. Patients will continue to receive durvalumab and tremelimumab with the same dose and schedule as they were treated with initially.

Additionally, 20 patients from the institutional database will be selected as exact matched control based on age, gender, tumor stage and Child-Pugh score. We will evaluate the objective response rate (ORR) in comparison to the study group, using McNamer paired-sample test.

Considering approximately 3-5 new patients with HCC seen through our tumor board and multidisciplinary liver cancer clinic per week, with an average of 300-400 DEB-TACE cases per year, we expect to finish the enrolment in 12 months of time.

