This is an open-label, single institution study of combination treatment of tremelimumab and durvalumab with trans-arterial chemoembolization with drug-eluting microsphere beads (DEB-TACE) in patients with intermediate stage HCC. The purpose of this study is to determine the safety and efficacy of durvalumab and tremelimumab in this population who are receiving DEB-TACE as standard of care. Patients who have intermediate stage HCC according to Barcelona Clinic Liver Cancer (BCLC) criteria, who are eligible for locoregional treatment with DEB-TACE will be enrolled. 20 HCC patients will undergo DEB-TACE, followed by durvalumab 1500mg q4weeks and tremelimumab 300mg once within 2 weeks. Patients will continue with durvalumab q4weeks until progression of disease or the end of study or maximum 13 cycles. Patients will have radiographic surveillance every 6-8 weeks from their last DEB-TACE, and if there is residual tumor that can be targeted, patients will receive repeat DEB-TACE.

All patients will have pre- and post-TACE biopsies during the first DEB-TACE treatment and post-immunotherapy infusion biopsy.

Patients who are clinically stable at an initial confirmed progression may continue to receive study treatment, after the first overall time point assessment of PD until PD is confirmed on a follow-up scan (confirmed PD) if they do not show any significant toxicities. Patients will get a confirmatory scan, following the assessment of PD, at the next scheduled visit. Patients that continue on study after an initial PD will continue to receive durvalumab and tremelimumab at the same dose and schedule as they were treated with initially.

In addition, we will have 20 patient data for patients with HCC from our institutional database as exact matched control based on age, gender, tumor stage and Child-pugh score. We will evaluate the objective response rate (ORR) in comparison to the study group, using McNemar paired-sample test.

Number of Centers: 1

Study Population: 20

Patients with intermediate stage HCC, defined by the Barcelona Clinic Liver Cancer (BCLC) stage B with compensated cirrhosis who would be eligible for liver-directed therapy (e.g. DEB-TACE) as standard treatment.

Inclusion Criteria:

- Patients with diagnosis of HCC either by high-resolution imaging (triple-phase CT or MRI) and/or by tumor biopsy.

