The safety evaluation will be based on the safety population, which includes all patients who receive DEB-TACE and at least one dose of either durvalumab or tremelimumab. Frequency of toxicity and adverse events will be summarized by type and grade. Primary efficacy analysis of best overall response will be based on response-evaluable population, which includes all patients who receive DEB-TACE and both durvalumab and tremelimumab, and have baseline scan and at least one on treatment scan or die without on treatment scan. Objective response rate, defined as the percent of patients who have CR or PR per mRECIST, will be estimated along with 95% confidence interval. Kaplan-Meier curves will be used to characterize progression-free survival (PFS) and overall survival. PFS rate at 6 month will be estimated from the Kaplan-Meier curve.

Objective response rate (ORR) from the exact matched control group (n=20) will be compared to the ORR of the study cohort using McNemar paired-sample test.

Sample Size Determination:

An optimal Simon two-stage design is planned. A total of 8 patients will be entered in the first stage. If ≤ 2 subjects respond, the treatment will be terminated and we will conclude the regimen is ineffective. If ≥ 3 subjects respond, then additional 12 patients will be studied. If a total of 8 or fewer subjects respond in stage one and two combined, the regimen is considered ineffective. If a total of 9 or more respond, we conclude the regimen is promising and warrants further study. The maximum sample size will be 20 evaluable patients. To account for 10% unevaluable patients who do not receive durvalumab/tremelimumab following DEB-TACE, or do not have any on treatment scans for reasons other than death, we plan to enroll 22 patients.

This design provides 90% power to detect a 30% absolute increase in ORR, from 30% to 60%, with one-sided type I error 0.1. The chance of stopping early for lack of efficacy at the interim analysis is 0.55, if the response rate is 30%.

STUDY SCHEMA

Figure 1: Schema

[figure not shown]

TABLE OF CONTENTS

PROTOCOL SYNOPSIS	3
STUDY SCHEMA.....	9
TABLE OF CONTENTS.....	10
LIST OF TABLES.....	13
LIST OF FIGURES	13
LIST OF APPENDICES.....	13
ABBREVIATIONS AND DEFINITION OF TERMS.....	14
1. INTRODUCTION	18
1.1 Disease background	18
1.1.1 Hepatocellular Carcinoma.....	18
1.1.2 Immunotherapies	18
1.1.3 Durvalumab	20
1.1.4 Tremelimumab	20
1.1.5 Durvalumab in combination with tremelimumab	20

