8.1.2 Treatment phase

Procedures to be conducted during the treatment phase of the study are presented in the Schedule of Assessments.

Patients will be treated with DEB-TACE. Transarterial chemoembolization is percutaneous procedure performed under conscious sedation. (See **Section 5.3** for details). Following DEB-TACE, patients will have surveillance imaging at 7 weeks, and if there are viable tumor lesions that can be targeted by DEB-TACE (either SD or PR), patients will be scheduled for another procedure. We estimate that patients may receive up to 4 DEB-TACE treatments in 1 year time of the study.

From the time of first DEB-TACE, patients will receive their first combined immune checkpoint inhibition in 2 weeks, and continue with q4week cycle schedule as described in detail in **Section 3.1**.

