11.1.2 Efficacy analysis set

Evaluable population for objective response includes all patients who receive DEB-TACE and both of durvalumab/tremelimumab, and have baseline scan with measurable disease, and either have at least one on treatment scan or die without any on treatment scans.

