11.2.2 Efficacy analyses

The primary endpoint is objective response. Objective response rate, defined as the percent of patients with at least one visit response of CR or PR via mRECIST and will be based on the Evaluable Population.

As a secondary endpoint, the response of non-target lesions will be described. Other secondary efficacy endpoints include duration of response, 6-month progression-free survival, and overall survival (OS). Duration of response is defined as date of having CR or PR to the date of progression per mRECIST among the patients who have CR or PR. Progression free survival will be defined as the time from the date of start of the treatment until the documentation of disease progression according to mRECIST or death due to any cause, whichever occurs first. Patients who have not progressed or died at the time of the analysis will be censored at the time of the latest date of assessment from their last evaluable mRECIST assessment. Kaplan-Meier

curves will be used to characterize PFS and OS, and 6-month PFS will be estimated from Kaplan-Meier.

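### Controls are matched on four baseline factors only, while study patients are also selected and scored after baseline, so the matched ORR comparison can favour the study group even if immunotherapy adds nothing

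*Combined protocol and SAP*

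**What the plan says.** **Controls.** The synopsis (Study Design) states "we will have 20 patient data for patients with HCC from our institutional database as exact matched control". Section 3 repeats the rule: "20 patients from the institutional database will be selected as exact matched control based on age, gender, tumor stage and Child-Pugh score". The synopsis (Statistical Methods and Data Analysis) gives the analysis: "Objective response rate (ORR) from the exact matched control group (n=20) will be compared to the ORR of the study cohort using McNemar paired-sample test". No other selection rule appears. The text does not say that controls had DEB-TACE, how many sessions they had, from what date they are followed, or which scans count. Section 11.2.2, which specifies the efficacy analyses, does not mention the comparison.

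**Study patients: selection after baseline.** Section 3 has patients seen 7-10 days after DEB-TACE. "If the patient does not have any ongoing new decompensation, they will proceed with a 2nd biopsy", and the first infusion follows two weeks after DEB-TACE. The efficacy set in Section 11.1.2 "includes all patients who receive DEB-TACE and both of durvalumab/tremelimumab, and have baseline scan with measurable disease", plus either an on-treatment scan or death without one. Under Section 4.4, patients lost after the first DEB-TACE, or judged unsuitable for the drugs because of medical complications, are replaced.

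**Study patients: scoring.** Section 11.2.2 defines ORR as the "percent of patients with at least one visit response of CR or PR via mRECIST". Section 3 repeats DEB-TACE every 8 weeks while there is residual tumor to target. Note a to the study schedule expects at least two sessions in most patients, and Section 8.1.2 adds: "We estimate that patients may receive up to 4 DEB-TACE treatments in 1 year time of the study".

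**The concern.** Matching at baseline balances what was known at baseline. It cannot balance a filter or a scoring rule that acts afterwards on one group only. There are two such differences here.

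- **Landmark.** A study patient who decompensates after the first session does not reach the infusion, leaves the ORR denominator and is replaced. No equivalent exclusion is written for controls.
- **Opportunity to respond.** A study patient is a responder if any one visit shows CR or PR, across scans at Week 6, Week 14 and then every three months, with DEB-TACE repeated in between. A control scored after a single session has fewer chances.

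Prior local therapy and failed systemic therapy are allowed in study patients (Section 4.1, criterion 4) but are not matching factors.

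Every study patient receives DEB-TACE, and the hypothesis is that checkpoint blockade adds to it. The matched analysis is the only place where individual DEB-TACE-era outcomes from the same institution could support that claim. If the groups differ in selection and scoring, a paired test cannot separate that difference from a drug effect. The control query and scan window could also be settled after the study results are known, in an open-label single-site trial.

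**Working it through.** **The plan's own figures.** Section 11.3 gives a Simon design: stop if 2 or fewer of 8 respond, and succeed with 9 or more of 20. Exact binomial calculation gives type I error 0.0999 at 30%, power 0.912 at 60% and early-stop probability 0.552, which agrees with the stated 0.1, 90% and 0.55. No alpha, sidedness or power is stated for McNemar, so two-sided 0.05 and independent pairs are assumed below. On that basis, 20 pairs give 34% power (exact) for a true 60% v 30%.

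**Inputs from the documents.** 30% ORR for standard DEB-TACE and 10% unevaluable (Section 11.3); 20 pairs (synopsis); two or more sessions in most patients (schedule note a); up to four in a year (Section 8.1.2).

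**Assumptions not in the documents.** The 30% applies after one session. A share c of remaining non-responders converts at each further session, with c = 10-20%. Controls are scored after one session. Immunotherapy has no effect.

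**Step 1: landmark alone.** If a share f is lost before infusion and would have responded at rate g, the ORR in those remaining is (0.30 − f·g)/(1 − f). With f = 0.10:
- g = 0: 0.30/0.90 = 33.3%
- g = 0.30: (0.30 − 0.03)/0.90 = 30.0%

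So the landmark adds between 0 and 3.3 points if those lost respond no better than average. The 10% also includes patients with no scan, so using it all as landmark loss is generous.

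**Step 2: any-visit scoring alone.** After k sessions, ever-response is 1 − 0.70·(1 − c)^(k−1).

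| Sessions scored | c = 10% | c = 15% | c = 20% |
|---|---|---|---|
| 1 | 30% | 30% | 30% |
| 2 | 37% | 40.5% | 44% |
| 3 | 43.3% | 49.4% | 55.2% |

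**Step 3: what the planned test does with this.** For independent pairs, the probability that only the study member responds is p_T(1 − p_C), and that only the control responds is p_C(1 − p_T). Enumerating all outcomes of 20 pairs gives the probability that McNemar declares the study group better:

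| Study v control ORR | Study only | Control only | Exact | Uncorrected |
|---|---|---|---|---|
| 30% v 30% | 0.210 | 0.210 | 1.0% | 2.2% |
| 40.5% v 30% (2 sessions) | 0.284 | 0.179 | 5% | 9% |
| 49.4% v 30% (3 sessions) | 0.346 | 0.152 | 14% | 21% |

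**Step 4: both together.** With f = 0.10 and g = 0, dividing the Step 2 rates by 0.90 gives 41-49% after two sessions and 48-61% after three (c = 10-20%). The exact McNemar rates are 5.6-13.5% and 12.5-37%.

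**With equal landmark and scoring,** the expected difference is zero and the exact rate returns to 1.0%.

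**The case against.** The strongest objection is that the documents are silent on controls, so no direction can be proved. This stands.

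- DEB-TACE is standard care at the same institution (Section 5.3), so controls may also have had repeat sessions. If they too are scored on their best scan, the larger component disappears.
- mRECIST scoring needs a follow-up scan. A control who decompensated early may never be selected, so controls may pass a landmark of their own. A reader might infer that such a control stays in as a non-responder; nothing in the text says so.
- Study patients who die unscanned after receiving both drugs remain in the denominator (Section 11.1.2), and patients who failed systemic therapy are admitted. Both can work against the study group.

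A reader might also infer that this is the trial's only comparison with TACE alone. It is not: the primary Simon test uses a 30% benchmark described as the DEB-TACE response rate (Section 11.3), and Section 2.3 lists a biomarker comparison with DEB-TACE only. The matched analysis is not among the stated objectives and drives no decision.

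On size, Section 11.3 does not tie the 30% to one session. If it is already a best response over a course, the Step 2 rates are too high. It is also tempting to quote the chance of an observed gap of 20 points or more: 0.55 for 49.4% v 30%, against 0.11 for equal rates. That is the probability of a raw gap, not of a significant result from the planned test.

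Finally, tumor stage and Child-Pugh score are matched, so part of eligibility is already covered. None of this removes the need for a common rule: the text as written allows a non-comparable contrast.

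**Conclusion.** The concern holds as a statement of what the comparison can do. Controls are selected on four baseline factors, while study patients are filtered after baseline and scored on any visit over repeated DEB-TACE. The only patient-level ORR comparison with controls can therefore favour the study group with no drug effect. That direction is plausible but not established.

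Repeated sessions with any-visit scoring are the larger source: 7-14 points after two sessions and 13-25 after three, under the stated assumptions about conversion, the 30% and control scoring. The landmark alone contributes at most 3.3 points at the protocol's 10% unevaluable share. In the mid-range case the planned test would wrongly favour the study group in about 5% or 14% of trials instead of 1%. The Simon decision rule does not depend on this comparison, but any claim of added benefit over TACE drawn from the matched controls would. The point should be fixed before controls are selected.

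**What to change.** In the synopsis and Section 3, require each control to have:

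1. DEB-TACE, with an index date at the session corresponding to study Week 0;
2. the main eligibility criteria at that date;
3. survival without ongoing new decompensation to Day 14;
4. the Section 11.1.2 evaluable definition without the study-drug condition: a baseline scan with measurable disease, and a later scan or death.

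Match also on prior TACE (yes/no), and use age bands if exact age leaves too few controls.

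For the paired comparison only, score both members by the same mRECIST rule over the same window: best response up to the Week 14 scan, plus response at the Week 6 scan, which precedes repeat DEB-TACE. The Week 6 result removes repeat sessions but reflects only about four weeks after the first infusion, so both are needed.

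Do not match on the number of DEB-TACE sessions. Repeat sessions are given only for residual tumor and stop at complete response, so matching on the count would select controls partly on outcome. Describe the number in both groups instead.

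Keep the primary ORR and the Simon rule unchanged.

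**Cost.** New wording, a stricter database query and possibly an mRECIST re-read of control scans; no new patients or study procedures. The control pool will be smaller and age matching coarser. The 300-400 DEB-TACE cases a year in Section 3 are not stated to be eligible individual patients, so the pool should be counted before the rule is fixed.
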